# 17.3.2 Secondary Pharmacokinetic Endpoints

Tmax will be analyzed using the non-parametric Wilcoxon signed-rank test.

 $AUC_{0-last}$ ,  $AUC_{0-4 \text{ weeks}}$ , and  $t_{1/2}$  will be analyzed using the methods applied for the primary PK parameters.

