### 8.2.2 Secondary Endpoints

- Change of secondary PK parameters (AUC0-4 weeks, AUC0-last, Tmax, and t1/2) of nemolizumab administered with AI or DCS
- Assessment of the immunogenicity (anti-drug antibodies, ADA) of nemolizumab administered with AI or DCS
- CCI

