### 9 INVESTIGATIONAL PLAN

### 9.1 **Description of Overall Study Design and Plan**

This is a randomized, multicenter, open-label, single-dose, parallel-group study in healthy adult subjects aged 18 to 65 years to assess the relative bioavailability of a 60-mg subcutaneous dose of nemolizumab administered with AI compared to DCS, stratified by injection site. The 60-mg dose will be administered as 2 successive subcutaneous injections of 30 mg (AI or DCS).

The study duration will be up to 16 weeks and consists of an up to 28-day screening period and a 12-week PK evaluation period.

The screening period will evaluate subject eligibility. At baseline, approximately 192 subjects will be randomized 1:1 to receive 60 mg nemolizumab delivered with either AI or DCS. Subjects will be further randomized 1:1:1 to receive injection in 1 of 3 injection sites, i.e., abdomen, front upper thigh, or outer upper arm. Approximately 32 subjects in each delivery group will be assigned to each injection site.

Subjects will receive a 60-mg dose of nemolizumab via 2 subcutaneous injections of 30 mg nemolizumab. Injections should be administered at the same location (i.e., abdomen, front upper thigh, or outer upper arm) and the same side with injection sites at least 1 inch (2.5 cm) apart. Blood samples will be collected before and after nemolizumab administration for up to 12 weeks postdose for determining the complete serum PK profile of nemolizumab.

[figure not shown]
A total of 21 blood samples will be collected, i.e., 1 before and 20 after nemolizumab administration (i.e., pre-dose, 12 hours, 24 hours, 3, 4, 5, 6, 7, 8, 9, 10, 11, 15, 22, 29, 36, 43, 50, 57, 71, and 85 days post-dose). Subjects will be confined to the study center for 1 night, from nemolizumab dosing (Day 0) to the morning after nemolizumab dosing (Day 1).

Refer to Figure 2 for an overview of the study design.

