# 9.2 Discussion of Study Design

This study will assess the relative bioavailability of a 60-mg subcutaneous dose of nemolizumab administered with AI compared to DCS, stratified by injection site, including abdomen, front upper thigh, or outer upper arm. Overall, a single-dose, open-label, parallel-group PK study in healthy adult subjects is deemed appropriate for this purpose.

The parallel-group design of this study is considered necessary due to the long terminal half-life of nemolizumab ranging from 12.6 to 16.5 days and is in line with the FDA guidance "Clinical Pharmacology Data to Support a Demonstration of Biosimilarity to a Reference Product" (Guideline 2016) and the corresponding European guideline (Guideline 2014).

In accordance with the same FDA guidance, the study plans a single-dose administration, since single-dose PK studies are generally more sensitive than steady-state studies in assessing any difference in rate and extent of release of the drug substance from the drug product into the systemic circulation. Furthermore, in the case of nemolizumab, repeated-dose studies demonstrated a limited systemic accumulation over time, with median accumulation below 2, and steady-state concentrations reached after the loading dose. This confirms that the PK profile of nemolizumab is not affected by the number of administrations and can be predicted from single-dose PK parameters.

The choice of heathy adult subjects is supported by the results of the Phase 1 study CIM001JP. Study CIM001JP showed that nemolizumab concentration-time profiles in AD patients and healthy subjects shared the same shape, being described in both groups by a one-compartment distribution model with linear elimination and first-order absorption. Overall, nemolizumab systemic exposure

increased in a dose-dependent manner in the dose range of 0.03 to 3 mg/kg. The only observed difference was a 23 to 26% reduced exposure in AD patients compared with healthy subjects. Owing to its low immunogenicity potential, there are no safety concerns associated with nemolizumab that will preclude investigation in healthy subjects. In addition, the type of disease does not have any effect on nemolizumab PK, as similar systemic exposure and similar PK profiles were observed in subjects with AD (Phase 2 study CIM003JG) and in subjects with PN (Phase 2 study SPR.115828) when treated with the same dose of 0.5 mg/kg.

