# 17.1 Determination of Sample Size

From previous studies conducted with nemolizumab, inter-subject standard deviation is expected to be approximately 38.5%, which provides an inter-subject variability CV for the primary PK parameters of 40%. A sample size of 96 subjects per arm (AI or DCS) should provide a 90% power of claiming the bioequivalence between AI and DCS administration within the range 80.00 to 125.00% for the primary PK parameters with the expected GMR of 0.95.

Approximately 192 healthy subjects are planned to be randomized in this study.

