# 17.3 Statistical Analysis of Pharmacokinetic Parameters

# 17.3.1 Primary Pharmacokinetic Endpoints

For the primary PK endpoint analyses, a linear mixed-effect model will assess the log transformed PK parameters (AUC $_{0\text{-inf}}$  and  $C_{max}$ ) of nemolizumab, with treatment (administration with AI or DCS) and injection site as fixed effects and subject as a random effect. Some clinically important baseline characteristics may also be included in the model. The AUC and  $C_{max}$  GMR between treatments (nemolizumab administered with AI [test] or DCS [reference]) after backtransformation and the corresponding 90% CI will be provided overall.

Acceptance criterion for bioequivalence is a 90% CI for the test/reference ratio of the geometric means of the parameters under consideration within the 80.00 to 125.00% range.

In addition, the GMR and 90% CI will be provided by injection site for information only.

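### Tmax is to be compared between two independent device groups with the Wilcoxon signed-rank test, a paired test that this parallel-group design cannot support

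*Protocol*

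**What the plan says.** Section 17.3.2 gives Tmax a test of its own: it "will be analyzed using the non-parametric Wilcoxon signed-rank test". The other parameters in that section (AUC0-last, AUC0-4 weeks and half-life) follow the model used for the primary parameters.

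Tmax is a named endpoint. Section 8.2.2 lists it under "Change of secondary PK parameters", for administration with AI or DCS.

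The design is stated just as plainly. Section 9.1: "This is a randomized, multicenter, open-label, single-dose, parallel-group study in healthy adult subjects", in which "approximately 192 subjects will be randomized 1:1 to receive 60 mg nemolizumab delivered with either AI or DCS". Section 11.3.1 repeats the allocation. Section 9.2 explains why no subject receives both devices: "The parallel-group design of this study is considered necessary due to the long terminal half-life of nemolizumab", which it puts at 12.6 to 16.5 days.

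**The concern.** The signed-rank test is a one-sample test on differences. It needs two values that belong together, such as two periods in one subject or two members of a matched pair. It suits a crossover study, and Section 9.2 rules a crossover out. Here the test has no differences to work on.

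Tmax bears on a question the study was set up to answer. Section 7.2 says the study addresses changes in injection depth, angle and time between the devices, and these could plausibly shift the timing of absorption. Section 9.2 concentrates sampling around the expected Tmax of 5 to 9 days. If the prespecified comparison cannot be carried out, someone must choose another after the fact. In an open-label study (Section 11.3.2) that choice is better fixed beforehand.

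**Working it through.** The plan states no figure for the Tmax comparison, so there is none to reproduce. The check is whether the data can feed the named test.

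**1. What each test needs**

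- *Signed-rank:* form D_i = X_i − Y_i for i = 1, …, n, rank |D_i|, and sum the ranks of the positive D_i. X and Y must share the index i. With 96 complete pairs and no zero differences or ties, the null mean of the sum is n(n+1)/4 = 96 × 97/4 = 2,328.
- *Rank-sum:* rank all n1 + n2 values together and sum the ranks in one arm. Only the arm label is needed. With 96 per arm the null mean is n1(n1+n2+1)/2 = 96 × 193/2 = 9,264.

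**2. What the design supplies**

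| Requirement of the signed-rank test | Protocol |
|---|---|
| Two Tmax values per subject | No: single dose, one device per subject (Sections 9.1, 11.3.1) |
| Matched AI and DCS subjects | No matching is defined; injection site is a stratum of about 32 per device, not a pair |
| Equal evaluable numbers in the arms | Not assured: treated subjects are not replaced (10.4), the PK population requires evaluable data (17.2), missing values are not imputed (17.6) |

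D_i is therefore undefined.

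**3. Could another reading rescue it?** A one-sample signed-rank test within one arm can be computed, but it asks whether Tmax is centred on zero. Tmax is always positive, so the answer is known in advance. In the simulated arm below, p is about 1.4 × 10⁻¹⁷. It says nothing about AI versus DCS.

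**4. What happens if pairs are invented**

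Assumed inputs: 96 independent subjects per arm, with Tmax on sampling days 3 to 11. The probabilities are:

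| Day | 3 | 4 | 5 | 6 | 7 | 8 | 9 | 10 | 11 |
|---|---|---|---|---|---|---|---|---|---|
| Arm A | 0.04 | 0.08 | 0.16 | 0.20 | 0.20 | 0.14 | 0.09 | 0.05 | 0.04 |
| Arm B | 0.03 | 0.06 | 0.12 | 0.16 | 0.20 | 0.18 | 0.12 | 0.08 | 0.05 |

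The means, Σ day × probability, are 6.71 and 7.16 days, an assumed shift of 0.45 day. One dataset was drawn and its values held fixed. Only the pairing was reshuffled, 2,000 times.

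| Test on the same 192 values | p |
|---|---|
| Rank-sum | 0.083 (one value) |
| Signed-rank, smallest over pairings | 0.013 |
| Signed-rank, median over pairings | 0.082 |
| Signed-rank, largest over pairings | 0.222 |
| Share of pairings with p < 0.05 | 10.5% |

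Another simulated dataset, log-normal around 7 days and rounded to the sampling grid, shows the same pattern: rank-sum p = 0.17, signed-rank p from 0.022 to 0.39 over 2,000 pairings.

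The median signed-rank p sits almost on the rank-sum value. Arbitrary pairing therefore does not push the result one way; it leaves the result undetermined. Because Tmax falls on a coarse grid, the number of zero differences that drop out also changes with the pairing.

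**The case against.** The best defence is that this is a naming slip with little reach. Tmax is secondary and has no margin or decision rule. The protocol labels Cmax, not Tmax, as its measure of absorption rate (Section 8.2.1). The decision rests on the primary parameters alone: "Acceptance criterion for bioequivalence is a 90% CI for the test/reference ratio of the geometric means", within 80.00 to 125.00%. The sample size in Section 17.1 is also set for the primary parameters. Tmax would still be listed and summarised by device under Section 16. Section 17 lets a later SAP override the protocol, so the test may be corrected there. And nobody is told to invent pairs; an analyst would more likely notice the problem and use the right test.

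All of this stands as a limit on the consequence. None of it makes the stated test applicable. The protocol did not leave the choice to the SAP; it named a specific test that conflicts with its own design. The SAP is not available here, so it cannot be assumed either to correct the error or to repeat it.

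The simulated p-values are also open to challenge. They depend on assumed distributions and differ between the two datasets. They show that the result depends on the pairing; they do not predict this trial's Tmax result.

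**Conclusion.** The concern holds. As written, Section 17.3.2 specifies for a named secondary endpoint a test that cannot compare the two devices in this design. That follows from the data structure alone, one Tmax per subject under one device with no matching, and needs no distributional assumption. The size of the pairing effect does rest on the simulation's assumptions: p from 0.013 to 0.222 against a single 0.083 in the specified example.

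The damage is confined to the Tmax comparison. The text should be corrected before analysis because it is plainly wrong and easily put right, not because the bioequivalence conclusion is at risk.

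**What to change.** Replace the Tmax sentence in Section 17.3.2 with wording such as:

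> Tmax will be compared between AI and DCS using the Wilcoxon rank-sum (Mann-Whitney) test, with the Hodges-Lehmann estimate of the location shift (AI minus DCS) and its 90% CI.

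The essential change is from signed-rank to rank-sum. The Hodges-Lehmann estimate is a useful addition because it gives the difference in days. It is the median of all AI-minus-DCS differences, which is not in general the difference between the two medians, so it should be described as a shift. A van Elteren version stratified by injection site would respect the stratified design and is an option.

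The cost is one phrase in the protocol, and in the SAP if it carries the same wording. No data, visits, subjects or primary analyses change.

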# 17.4 Safety Analysis

**Adverse Events:** All reported AEs will be coded using the most recent version of MedDRA. TEAEs, defined as those AEs after the first administration of study treatment until last study visit, will be tabulated in frequency tables by System Organ Class and Preferred Term. Additional summary tables will be provided for SAEs, AEs related to the study drug(s) (reasonable possibility, no reasonable possibility), AEs related to the study procedure, AESIs, and AEs leading to treatment discontinuation and study withdrawal. For an AE, a subject will be counted once even if he/she has experienced multiple episodes of that AE.

Pretreatment AEs will be listed separately.

Clinical Laboratory: Laboratory data (absolute values and change from baseline) will be summarized by visit and treatment group. In addition, the number and percentage of subjects below, within, and above the laboratory reference ranges and the number and percentage of subjects who met criteria of potential clinically significant value will be summarized by treatment group. Shift tables will be generated using the reference ranges. Reference ranges will be provided in the laboratory manual.

**Vital Signs:** All vital signs and weight data (absolute values and change from baseline) will be summarized by visit and treatment group. In addition, the number and percent of subjects with clinically significant abnormal values (of clinical concern as identified by the investigator) will be summarized by treatment group.

**12-Lead Electrocardiogram:** The number and percentage of subjects with ECGs that are abnormal/clinically significant and abnormal/not clinically significant will be displayed by treatment at each visit.

**Concomitant Medications:** Prior and concomitant medications will be coded according to the most recent version of the World Health Organization Drug Dictionary Enhanced for Concomitant Medication and summarized.

## 17.5 **Anti-Drug Antibody Analysis**

The incidence of positive ADA results will be summarized and plotted (absolute occurrence, percent of subjects, and treatment-emergent ADA) in the SAF.

## **Handling of Missing Data** 17.6

The statistical procedure will be conducted without imputing values to the missing observations.

## STUDY MANAGEMENT

## 18.1 **Approval and Consent**

#### 18.1.1 **Regulatory Guidelines**

This study will be conducted under the accepted version of the Declaration of Helsinki and/or all relevant regulations, as set forth in Parts 50, 56, 312, Subpart D, of Title 21 of the US Code of Federal Regulations (CFR), in compliance with International Council for Harmonisation (ICH) and Good Clinical Practice (GCP) guidelines, and according to the appropriate regulatory requirements in the countries where the study was conducted.

## 18.1.2 Institutional Review Board/Independent Ethics Committee Regulatory Guidelines

Conduct of the study must be approved by an appropriately constituted IEC/IRB. Approval is required for the study protocol, protocol amendments (if applicable), IB, ICFs, recruitment material and subject information sheets and other subject-facing material.

#### 18.1.3 **Informed Consent**

For each study subject, written informed consent will be obtained before any protocol-related activities. As part of this procedure, the principal investigator or designee must explain orally and in writing the nature of the study, its purpose, procedures, expected duration, alternative therapy available, and the benefits and risks involved in study participation. The subject should be informed that he/she may withdraw from the study at any time, and the subject will receive all information required by local regulations and guidelines for ICH. The principal investigator will provide the Sponsor or its representative with a copy of the IEC-/IRB-approved ICF before the start of the study.

#### 18.2 **Data Management**

The designated CRO will be responsible for activities associated with the data management of this study. This will include, but is not limited to, setting up a relevant database and data transfer mechanisms, along with validation of data and resolution of queries. All data management activities will be detailed in the data management plan.

Study centers will enter data directly into an electronic data capture (EDC) system by completing the eCRF via a secure internet connection. Data entered into the eCRF must be verifiable against source documents at the study center. Data to be recorded directly on the eCRF will be identified and the eCRF will be considered the source document. Any changes to the data entered into the EDC system will be recorded in the audit trail.

#### 18.3 **Source Documents**

Source documents are considered all information in original records and certified copies of original records of clinical findings, observations, data, or other activities in a clinical study necessary for the reconstruction and evaluation of the study. The investigator will provide direct access to source documents and/or source data in the facilitation of study-related monitoring, audits, review by IECs/IRBs, and regulatory inspections.

The investigator/institution should maintain adequate and accurate source documents and study records that include all pertinent observations on each of the site's study subjects.

Source data should be attributable, legible, contemporaneous, original, accurate, and complete. Changes to source data should be traceable, not obscure the original entry, and be explained if necessary.

Sponsor monitors, auditors, and regulatory inspectors should have direct access to source data.

#### 18.5 **Monitoring**

The study will be monitored according to the monitoring plan to ensure that it is conducted and documented properly according to the protocol, GCP, and all applicable regulatory requirements.

Monitoring visits and contacts will be made at appropriate times during the study. The principal investigator will assure he/she and adequate site personnel are available throughout the study to collaborate with clinical monitors. Clinical monitors must have direct access to source documentation to check the completeness, clarity, and consistency of the data recorded in the eCRFs for each subject.

The investigator will provide to the clinical monitor all source documents and medical records necessary to review protocol adherence and eCRFs. In addition, the investigator will work closely with the clinical monitor and, as needed, provide them appropriate evidence that the study is being conducted under the protocol, applicable regulations, and GCP guidelines.

#### 18.6 **Quality Control and Quality Assurance**

The Sponsor or its designee will perform the quality assurance and quality control activities of this study; however, responsibility for the accuracy, completeness, security, and reliability of the study data presented to the Sponsor lies with the investigator generating the data.

This document is confidential.

## 18.7 Protocol Amendment and Protocol Deviation

# 18.7.1 Protocol Amendment

Amendments to the protocol that entail corrections of typographical errors, clarifications of confusing wording, changes in study personnel, and minor modifications that do not affect the safety of subjects or the conduct of the study will be classed as administrative amendments and will be submitted to the IEC/IRB for information only. The Sponsor will ensure that acknowledgment is received and filed. Amendments classed as substantial amendments must be submitted to the appropriate regulatory authorities and the IECs/IRBs for approval and will not be implemented at sites until such approvals are received other than with an urgent safety measure.

## 18.7.2 Protocol Deviation

Should a protocol deviation occur, the Sponsor must be informed soon. Protocol deviations and/or violations and the reasons they occurred will be included in the clinical study report. Protocol deviations will be reported to the IRB/IEC and under applicable regulatory authority mandates.

Changes that involve only logistical or administrative changes to the clinical study protocol are authorized. The investigator should document and explain any deviation from the clinical study protocol. Major deviations are categorized into these categories:

- Eligibility deviations (inclusion/exclusion criteria)
- Improper reconstitution and administration of study medication
- Non-compliance with study medication per the investigator's discretion
- Non-compliance with study procedures if the consequence of non-compliance would compromise either the subject's safety and/or the study integrity, primary endpoint, and/or is not in line with GCP/ICH guidelines
- Use of prohibited concomitant therapies

All protocol deviations will be identified, evaluated, and closed before the respective database lock (final analysis) and will be described in the clinical study report. Protocol deviations incurred because of the COVID-19 pandemic should be specifically recorded as a COVID-19 deviation. Further details of protocol deviations will be provided in the Protocol Deviation and Non-Compliance Management Plan.

## 18.8 Ethical Considerations

This study will be conducted under this protocol, the accepted version of the Declaration of Helsinki and/or all federal regulations, as set forth in Parts 50, 56, 312, Subpart D, of Title 21 of the CFR; EU 536/2014, Annex 1, D, 17 (a); and in compliance with GCP guidelines.

IECs/IRBs will review and approve this protocol and the ICF. All subjects must give written informed consent before participation in the study.

# 18.10 Publication Policy/Disclosure of Data

Both the use of data and the publication policy are detailed within the clinical study agreement. Intellectual property rights (and related matters) generated by the investigator and others performing the clinical study will be subject to the terms of a clinical study agreement agreed between the institution and the Sponsor or their designee.

Regarding such rights, the Sponsor or its designee will solely own all rights and interests in any materials, data, and intellectual property rights developed by investigators and others performing the clinical study described in this protocol, subject to the terms of any such agreement. To facilitate such ownership, investigators must assign all such inventions either to their institution or directly to the Sponsor or its designee, as set forth in the clinical study agreement.

